Multi-center, two-arm, prospective, Phase II, open label, randomized controlled trial.

Study Population

Hospitalized COVID-19 patients fulfilling the inclusion and exclusion criteria, and admitted for care at COVID-19 management facilities in India will be eligible for inclusion in the trial.

Inclusion Criteria

1. Patients admitted with RT-PCR confirmed COVID-19 illness.
2. Age > 18 years
3. Written informed consent
4. Has any of the two
 - a. PaO₂/ FiO₂ <300
 - b. Respiratory Rate > 24/min and SaO₂ ≤ 93% on room air

Exclusion criteria

1. Pregnant women
2. Breastfeeding women

3. Known hypersensitivity to blood products
4. Receipt of Pooled Immunoglobulin in last 30 days
5. Critically ill patients:
 - a. P/F ratio <200 (moderate - severe ARDS)
 - b. Shock (Requiring Vasopressor to maintain a MAP \geq 65mmHg or MAP below 65)
6. Participating in any other clinical trial
7. Clinical status precluding infusion of blood products

Assessment of donor for eligibility

COVID-19 convalescent plasma will be collected from recovered individuals if they are eligible to donate blood. Considerations for assessment of donor for eligibility are outlined in the section on convalescent plasma.

Sample Size

For sample size calculation, we considered that given the standard of care, 18% of patients would succumb to COVID-19 infections.[5] We considered a relative effectiveness of 50% for sample size calculations. We calculated sample size using the PASS v11.0 software.[42]

Group sample sizes of 226 in the intervention group and 226 in the control group achieve 80% power to detect an absolute difference of -0.09 between the group proportions. The proportion of participants meeting the primary outcome in group one (the treatment group) is assumed to be 0.18 under the null hypothesis and 0.09 under the alternative hypothesis. The proportion of participants in group two (the control group) who meet the primary outcome is assumed to be 0.18 based on current evidence.[5] The test statistic used is the two-sided Z test with pooled variance. The significance level of the test was targeted at 0.05, with a power of 0.8.

Primary Outcomes

The primary outcome is a composite measure of the avoidance of -

1. Progression to severe ARDS (P/F ratio <100) and
2. All-cause Mortality at 28 days

Secondary Outcomes

1. Time to symptom resolution
 - a. Fever
 - b. Shortness of Breath
 - c. Fatigue
2. Hospital length of stay
3. Change in SOFA pre and post transfusion

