4. Duration of respiratory support required
 - a. Duration of Invasive Mechanical Ventilation
 - b. Duration of Non-Invasive

5. Radiological improvement
6. Adverse events (AE) associated with transfusion
7. To measure the change in RNA levels (Ct values) of SARS-CoV-2 from RT-PCR [Time Frame: Days 0, 1, 3, and 7 after transfusion]
8. Correlation between Viral neutralization titer and Elisa antibody Assay
9. Correlation between titers in donor plasma and IgG titer on transfusion
10. Levels of bio-markers pre and post transfusion
11. Need of Vasopressor use
12. Pre and post transfusion antibody titers

Other Exploratory Endpoints

1. Cumulative incidence of serious adverse events during the study period: transfusion reaction (fever, rash), transfusion related acute lung injury (TRALI), transfusion associated circulatory overload (TACO), transfusion related infection
2. Rates and duration of SARS-CoV-2 PCR positivity (RT-PCR) from days 0 and if further available.

Analysis Plan

Baseline data about the demography, clinical presentations, ongoing medical therapy, and clinical history of participants in both arms will be collected and compared. Response to convalescent plasma will be coded as a binary outcome – based on whether the composite primary end point is met or not. Adverse events associated with infusion of convalescent plasma will also be descriptively summarized and compared with the adverse events experienced by participants receiving standard of care.

The objective response rate, defined as the proportion of participants successfully meeting the primary end points, will also be reported, along with a two-sided 95% confidence interval calculated using the Clopper-Pearson method.[45] This will be compared between the intervention and control groups.

Participants who drop off from the treatment arm prior to evaluation of post-intervention response will be considered as non-responders, regardless of the discontinuation reasons, and will be included in the intention to treat analysis. Comparison between group response rates will be analyzed and reported.

Study Procedures:

	Screen	Baseline	Intervention (Convalescent Plasma infusion)	Follow-up				
Day	-1 to 0	0	0	1	3	7	14	28
Pre-Intervention Screening								
Eligibility screening and Informed Consent	x							

Demographic and Medical history	x							
SARS-CoV-2 RT-PCR test for eligibility	x							
Pregnancy test	x							
ABO	x							
Study Intervention								
Symptom checking	x	x	x	x	x	x	x	x

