Indicative list of supplies/logistics necessary to conduct this study.

SI No	Item name
1	Anti-A
2	Anti-B
3	Anti-D
4	Antibody screen
5	Complete blood count
6	Serology (HIV, HBV, HCV, Syphilis & malaria)
7	NAT test (HIV, HBV & HCV)
8	Rapid IgG and IgM tests for COVID-19
9	IgM ELISA
10	IgG ELISA
11	Plasmapheresis disposable kit
12	Transfer bags
13	EDTA vials
14	Plain vials
15	20ml syringes
16	PPE kits
17	ELISA reader and washer
18	BBR-cum-freezer
19	Biosafety cabinet type 2
20	Donor Transport
21	Staff (technician / research associate)

Safety Assessments and Reporting

Definition of adverse event

An Adverse Event/Experience [AE] is any untoward medical occurrence in a participant undergoing TPE, is one which does not necessarily have a causal relationship with the TPE procedure. It can be any unfavorable and unintended sign, symptom, or disease, which is temporally associated with the use of convalescent plasma, whether or not considered to be causally related to convalescent plasma.

A Serious Adverse Event [SAE] is any untoward medical occurrence, at any point during convalescent plasma, results in:

- Death
- A life-threatening condition. This means any event in which the participant is at risk of death; it does not refer to a condition, which, with increasing severity, may result in death.
- Significant disability

Other medically significant outcomes, which may not result in any of the above, but may jeopardize the well-being of the participant, requiring greater degrees of medical or surgical interventions to prevent one of the outcomes listed above.

Data Management

Data Management Responsibilities

The Investigators will be responsible for assuring completeness, accuracy and timely collection of data. Case Record Forms (CRFs) should support the data entered in the electronic data capture system. They will be signed and dated by the person filling out the forms, and the investigator reviewing the same. Data will be reviewed by the Investigator and co-signed. Data management will be undertaken by ICMR-National Institute of Epidemiology.

Data Capture Methods

Paper CRFs will be used to collect data. The data will then be entered on an electronic system. A data entry system with electronic tracking, password restricted access, audit trail, with time and date stamps on data entry and edits, will be developed.

Types of Data

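### The SAE criteria omit readmission and prolonged hospital stay, so outside the transfusion events listed by type such harm is either non-serious or a matter of judgement in an open-label trial

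*Protocol*

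**What the plan says.** The SAE definition stands in the Protocol under the second Safety Assessments and Reporting heading, in Definition of adverse event. Its stem reads: "A Serious Adverse Event [SAE] is any untoward medical occurrence, at any point during convalescent plasma, results in". Three outcomes follow:

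- death;
- "A life-threatening condition. This means any event in which the participant is at risk of death", with a rider that excludes a condition which would become fatal only if it worsened;
- "Significant disability".

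A closing sentence adds "Other medically significant outcomes, which may not result in any of the above, but may jeopardize the well-being of the participant", with the limiting condition "requiring greater degrees of medical or surgical interventions to prevent one of the outcomes listed above".

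Other parts of the Protocol bear on this:

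- Study Design: "Multi-center, two-arm, prospective, Phase II, open label, randomized controlled trial". Study Population: the participants are inpatients at entry.
- Secondary Outcomes includes "Hospital length of stay", with no link to an adverse event.
- Other Exploratory Endpoints (1) is "Cumulative incidence of serious adverse events during the study period". After a colon it names transfusion reaction (with fever and rash as instances), TRALI, TACO and transfusion-related infection.
- The Study Procedures table has adverse event monitoring on the infusion day and on days 1, 3, 7, 14 and 28.
- Hypothesis and Objectives makes safety part of the primary objective, and the Analysis Plan compares adverse events between plasma and standard of care.

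**The concern.** In patients who are already in hospital and are followed to day 28, a readmission or a stay lengthened by an event is a natural marker of serious non-fatal harm. Neither is a seriousness criterion here. Such an event can reach the SAE count only through the catch-all, whose test is whether well-being may be jeopardised and whether more intervention was needed to head off death, a threat to life or disability.

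Two things are at stake. Some non-fatal serious harm may not be counted in either arm. And where an event could go either way, the person deciding may know the allocation, so the arms can be classified differently for the same events.

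**Working it through.** The plan states no SAE rate, so there is no figure to reproduce. The 226 per arm is set for the primary outcome and does not enter. The check is a comparison of the texts.

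**Step 1: run a test case through the definition.** Take an event, not one of the named transfusion events, that leads to a readmission on day 20 or adds days to the stay, and that is neither fatal, life-threatening nor disabling.

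| Criterion | Met? |
|---|---|
| Death | No |
| Life-threatening condition | No; the rider also excludes conditions that are dangerous only if they worsen |
| Significant disability | No |
| Catch-all | Only if judged to jeopardise well-being **and** to need more intervention to prevent one of the three outcomes above |

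The event is either not an SAE or is one by judgement.

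**Step 2: look for the criterion elsewhere.** Length of stay appears only as a secondary outcome. No section makes readmission or prolonged stay a mark of seriousness.

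**Step 3: who judges?** The Protocol does not name the assessor. Data Management Responsibilities has the investigator review and co-sign the data, the trial is open label, and no blinded review of seriousness is described. That the assessor knows the arm is a reasonable inference, not a stated fact.

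**Step 4: read the stem.** It ties an SAE to the plasma. Taken literally, it excludes events after the plasma treatment and every control-arm event, whatever criteria follow. That does not fit monitoring to day 28 or a comparison with standard of care. A day-20 readmission would fail here before the criteria are reached.

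**Step 5: set the definition beside the exploratory endpoint.** The endpoint names four kinds of transfusion event as SAEs with no test of seriousness, so a mild rash counts there and does not meet the definition. The Protocol does not say whether the four are a complete list or examples. If complete, no other event enters the endpoint at all. If examples, every other event must pass the definition and Step 1 applies. The named events follow transfusion, so they would arise mainly in the plasma arm and do not supply a criterion that works alike in both arms.

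**Step 6: size.** Let *r* be the proportion of patients, equal in both arms, with an event of the Step 1 kind, and *p*(plasma) and *p*(control) the proportions of those events that are called serious. Then

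spurious difference in SAE incidence = *r* × [*p*(plasma) − *p*(control)]

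undercount in an arm = *r* × (1 − *p*)

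None of *r*, *p*(plasma) and *p*(control) stands in the documents, so neither quantity can be calculated from them.

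**The case against.** The strongest reply is that the gap is small and partly filled. The exploratory endpoint already counts transfusion reactions, TRALI, TACO and transfusion-related infection by type, and so catches more of these than a prolongation criterion would. The omitted events are still recorded as adverse events to day 28, length of stay is measured, and life-threatening and disabling events are covered. The catch-all is an open category. SAE incidence is exploratory, and adverse events are summarised descriptively. All of this stands. It limits the point to classification, and it means that the point does not apply to the named transfusion events.

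A second reply is that the remedy is less objective than it looks. Whether an event prolonged the stay of a patient already in hospital with COVID-19 is a causal judgement, made by the same open-label staff. That stands too: readmission is close to a plain fact, whereas a prolongation criterion reduces discretion without removing it.

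A third is that a new criterion alone would achieve little under the present stem. This is correct, and the fix has to include the stem.

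None of these replies supplies the missing criterion for other events, which is where nearly all control-arm events fall.

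**Conclusion.** The definition is badly fixed on this point and should be changed. Outside the named transfusion events, harm whose only serious feature is readmission or a longer stay is non-serious or depends on judgement. Non-fatal serious harm can be under-counted, and the SAE comparison is open to differential classification. The second consequence rests on the inference that whoever judges seriousness knows the arm.

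Three stronger readings are tempting, and the documents do not support them:

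- *Any reaction that lengthens the stay is serious only if an unblinded investigator says so.* The named transfusion events count by type, and the assessor is not identified.
- *The bias can be put at a figure.* For example, *r* of 4% to 10% with 75% of events called serious on plasma and 50% on control gives 0.04 × 0.25 = 1.0 to 0.10 × 0.25 = 2.5 percentage points. All of these rates are assumptions. Reversing the split reverses the sign, and an equal split gives zero. The result only restates the assumed split.
- *Most of the monitoring falls after discharge.* The documents give no discharge times.

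The impact is limited to the exploratory SAE endpoint and the safety comparison. The primary outcome and the sample size are unaffected.

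**What to change.** Make three changes together.

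1. Add to the SAE list: *requires readmission to hospital, or prolongs the existing hospitalisation because of the event (not for expected COVID-19 care, isolation or administrative reasons)*. Record the two parts separately, since only the first is close to objective.
2. Reword the stem so that it covers participants of both arms from randomisation to day 28, in line with the monitoring schedule. The Study Procedures table puts randomisation in the screening column and starts adverse event monitoring on the infusion day, so the monitoring row needs an entry from randomisation.
3. Reconcile the criteria with Other Exploratory Endpoints (1). Say whether the four kinds of transfusion event are SAEs regardless of seriousness or are events of interest reported separately, and whether the list is complete.

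The cost is some rewording in two sections, one entry in the schedule, two tick-boxes on the adverse event form, and more SAE reports to process.
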